#### Best overall response

Best overall response (see section 7.7.8) at the end of treatment will be summarized using descriptive methods described in section 8.1. The summary table will include frequencies and percentages for each response category (CR, PR, SD, etc. described in 11.2).

Table	
14.6.4	Best overall response

### 8.4.4 Response based on IWG 2023

Response based on the updated IWG 2023 criteria at visit 9 will be analyzed only for MDS population. The summary will be based on descriptive methods, as described above.

Table	
14.6.5	Response based on the updated IWG 2023

### 8.4.5 HRQoL

Health-Related Quality of Life (HRQoL) will be accessed using EORTC QLQ-C30, version 3. The raw score for global health status / QoL, functional scales and symptom scales / items (as defined on 7.7.10 ) will be summarized with descriptive statistics by visit. Moreover, the sub scores (linear transformation to 0 to 100) will also be provided.

Table	
14.6.6	Health-Related Quality of Life
Listing	
16.6.6	Health-Related Quality of Life

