BM cytology assessment (local) ¹⁰			x					x ¹⁴	x ¹⁵
Serum chemistry (local)	x		x		x		x	x	x
Automated CBC (local)	x	x	x	x	x	x	x	x	x
Cytogenetics (local)			x					x	

Part 2c – extension treatment phase, from cycle 5 (non-responders with stable or controlled disease who continue treatment at the investigator's discretion)

VISIT NO.	██████████
Study Day (± 3d)	████████████████████
Study Week	██████
Cycle	██████████
Concomitant MDS/AML specific medication	X
Pregnancy test	X
Imetelstat administration and drug account	X ¹⁶
Toxicity/AE assessment	X
LOCAL LABORATORY: Response assessment ¹⁷	X ¹⁸
CBC with differential (local)	X ¹⁸
PB blast assessment (local)	X ¹⁸
BM cytology assessment (local)	X ¹⁸

¹⁶ The dosing frequency for imetelstat (every ■ weeks or every ■ weeks) for these subjects will be determined at the discretion of the investigator.

17 Response assessment will be performed based on the combined response assessment criteria for MDS and AML based on IWG 2018 criteria (MDS) and the criteria of the European LeukemiaNet (AML). Additionally, the BM blast level at each response assessment will be the basis for deciding the frequency of treatment of imetelstat (every █ weeks or every █ weeks) until the next response assessment.

¹⁸ Optional response assessment and lab measurements to be done according to standard of care and/or only in case needed to assess and follow-up on (S)AEs and dose modifications

Part 3 – EOT and follow-up period (all patients)

VISIT NO.	██████ ██████ ██████	████ ██████ ██████	██████████ ██████ ██████████ ██████████	██████	██████████
Study Day (± 3d)	██████	██████	██████	██████████	██████████
Study Week	██████	██████	██████	██████	██████
Informed consent					
In- / exclusion criteria ³					
MDS/AML related medical history					
Concomitant MDS/AML specific medication	x	x	x	x	
Physical examination, vitals	x	x	x	x	
BMI	x	x	x	x	
Pregnancy test ⁴	x	x	x	x	
Toxicity/AE assessment	x	x	x	x	
Quality of life (QoL, EORTC QLQ-C30)	x	x	x		
Information on current state of condition / survival status	x	x	x	x	x
Central assessments / correlative analyses (EU: Leipzig, AUS: QIMRB, Brisbane)					
Bone marrow aspiration (5 mL sodium heparinized in separate tubes for central assessments)		x ²²			
Peripheral blood sampling for central assessments (10 mL sodium heparinized blood in separate tubes for central assessments)		x ²²			
Genetic profiling (NGS) at central laboratories		x			
MRD analyses at central laboratories					

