8.1.3 Treatment period

The subject will start treatment upon confirmation of eligibility. The subject must start treatment within [REDACTED] of signing the ICF. If screening assessments are performed within 72 hours of C1D1, serum chemistry laboratory assessments and physical examinations need not be repeated at C1D1 with the exception of automated CBC.

If subject completed the QoL EORTC QLQ-C30 questionnaire at Screening within 2 weeks of C1D1, it does not have to be repeated at C1D1. If performed on C1D1, it should be completed prior to IMP administration.

On dosing days, local laboratory levels should be assessed prior to each IMP administration to ensure dose modification rules are followed as outlined in section 7.3 Dose modification guidelines.

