## 7. Data Handling

### 7.1 Handling of Missing Data and Outliers

If outliers, i.e., impossible, or very implausible values, occur, queries will be raised to the investigator who will either correct or confirm the value. If the value is confirmed, the analysis will be carried out with the outlier included. Complete exclusion of values should only be done in exceptional cases and is only valid for impossible and very implausible values with obvious justification. The decision to exclude data points from the statistical analysis is the joint responsibility of the sponsor, and the statistician. Outliers will be documented and, if applicable, their exclusion from analysis will be justified in the clinical study report.

Missing data will not be imputed.

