### 7.7.1 Baseline Definition and Change from Baseline

In general, the baseline value of an assessment is defined as the last available measurement before start of treatment. For vital signs (except for height, weight and BMI), physical examination, serum chemistry and automated CBC, baseline is the last available measurement before visit 1 (cycle 1, week 1). For the remaining variables baseline values are collected at the screening visit.

Change from baseline will be calculated as follows only for continuous variables:

$$\text{Change from baseline} = (\text{post-baseline value}) - (\text{baseline value})$$

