## 8. Statistical Analysis Methods

### 8.1 Descriptive Statistics

The default summary statistics for quantitative variables will be the number of non-missing observations (n) and the number of missing observations (miss) as well as arithmetic mean, standard deviation (STD), minimum (min), median, and maximum (max).

For categorical variables, the number (n) and percentage (%) of subjects per category will be the default summary presentation, and, if applicable, the number of missing values is provided in a “missing” category. For the number of missing values, all subjects in the respective study population will be counted. Percentages will be calculated using a denominator of all subjects in a specified population with non-missing data. If necessary, the denominator will be specified in a footnote to the tables for clarification.

Visit related descriptive statistics will be provided only for visits with more than 5 non-missing observations. Results from visits with 5 or less non-missing observation will be only listed.

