### 8.5.4 Other safety assessments

Clinical chemistry, vital signs, Automated complete blood count and BM Cytology Assessment (see 6.2.3) will be summarized descriptively by visit (using the visit labelling from the SoA (see 2.4)) for the original data as well as for the difference to baseline (as defined in 7.7.1). Patients with laboratory values outside of the normal reference range at any postbaseline assessment will be listed.

Table	
14.9.1	Clinical chemistry
14.9.2	Vital signs
14.9.3	Automated complete blood count
14.9.4.1	BM Cytology Assessment (continuous)
14.9.4.2	BM Cytology Assessment (categorical)
Listing	
16.9.1	Clinical chemistry

16.9.2	Vital signs
16.9.3	Automated complete blood count
16.9.4	BM Cytology Assessment
16.9.5	CBC with differential
16.9.6	Cytogenetic Analysis
16.9.7	Physical examination

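### QLQ-C30 scores are summarised by visit without within-patient change from baseline, so selective dropout can make later visits look better than the patients' own course

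*SAP*

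**What the plan says.** **Planned summary.** SAP 8.4.5 and protocol 10.8.2.6 use the same phrase: the raw scores "will be summarized with descriptive statistics by visit". The 0-100 scores are provided as well. The outputs are Table 14.6.6 and Listing 16.6.6, on the FAS and by cohort.

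**Content of the summary.** Besides n, the default in SAP 8.1 is the "number of missing observations (miss) as well as arithmetic mean, standard deviation (STD), minimum (min), median, and maximum (max". SAP 8.1 also sets a floor: "Visit related descriptive statistics will be provided only for visits with more than 5 non-missing observations". Smaller visits are only listed.

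**Change from baseline.** SAP 7.7.1 gives a general rule: "Change from baseline will be calculated as follows only for continuous variables". SAP 8.5.4 applies it to chemistry, vital signs, automated blood count and marrow cytology, which are summarised "for the original data as well as for the difference to baseline (as defined in 7.7.1". SAP 8.4.5 does not call on it.

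**Missing data.** SAP 7.1: "Missing data will not be imputed".

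**Who is asked, and when** (protocol VII, repeated in SAP 2.4):
- Parts 2a and 2b, the extension schedules for responders, have a filled QoL row.
- Part 2c, for "non-responders with stable or controlled disease who continue treatment at the investigator's discretion", has no QoL row.
- Part 3, for all patients, has QoL ticked in the first three of five columns. The column headers are redacted; from the footnotes I read those three as versions of the EOT visit.
- Protocol 8.1.3 waives the form at first dosing when there is a recent "questionnaire at Screening within 2 weeks of C1D1, it does not have to be repeated at C1D1".

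**The concern.** Quality of life is a named secondary efficacy endpoint. A by-visit table is naturally read from left to right as a course over time, but that reading is sound only if the rows describe the same patients.

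Here they do not. Patients are lost to death, to the rule that stops treatment for marrow progression at the assessment after 4 doses, and to non-response at visit 9. If those who leave started with poorer scores, the remaining group has a better average whatever happens to each patient. Better means higher global health and transformed functional scores, and lower symptom scores. Raw functional scores run the other way (SAP 7.7.10), and SAP 8.4.5 tabulates those too.

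Two details make the baseline less firm. The visit 1 row may hold only part of the cohort because of the waiver. SAP 7.7.1 first defines baseline as the last value before treatment and then assigns the remaining variables, which would include QoL, to the screening visit. For a patient who fills in the form at both visits, these are different values.

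**Working it through.** The documents state no score, SD, decline or retention figure for QoL, so there is no planned figure to reproduce. All score inputs below are assumptions.

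**1. Shift in a visit mean under selective retention**

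Inputs (assumed): SD of baseline score 20; every patient has an expected change of -3; correlation r between baseline score and staying on study 0.3 or 0.5; fraction retained q.

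Formula: visit mean minus all-patient baseline mean = r × 20 × φ(z)/q - 3, where z cuts off the upper fraction q of a standard normal. The factor φ(z)/q is 0.644, 0.966 and 1.271 at q = 0.60, 0.40 and 0.25.

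| Retained | r = 0.3 | r = 0.5 | Paired change |
|---|---|---|---|
| 60% | 6 × 0.644 - 3 = +0.9 | 10 × 0.644 - 3 = +3.4 | -3 |
| 40% | 6 × 0.966 - 3 = +2.8 | 10 × 0.966 - 3 = +6.7 | -3 |
| 25% | 6 × 1.271 - 3 = +4.6 | 10 × 1.271 - 3 = +9.7 | -3 |

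A simulation of 200,000 patients agreed to within 0.1 point (+0.9 and +3.5 at 60%).

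**2. Is 60% retained plausible by visit 9?**

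Protocol 1.1.1 cites a median OS of 4 to 5.6 months for higher-risk MDS after HMA progression. Assuming exponential survival, with 16 weeks = 3.68 months, the fraction alive is exp(-ln 2 × 3.68/median): 0.53 at 4 months and 0.63 at 5.6 months. The trial also enrols AML and HMA-intolerant patients, so this is a rough guide only. Patients who progress early come off in addition.

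**3. Which rows would be shown?**

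The size of cohort 2 is redacted. As an illustration I take 20 to 22 patients (22 is the enrolment figure in protocol 10.3).
- At 60% retained, 12 to 13 patients contribute, so the row is tabulated.
- At 25% retained, 5.0 to 5.5 patients contribute, which is at the SAP 8.1 floor, so the row would often be listed only.
- For a responder-only visit at the planned 20% response rate, with every responder completing the form, the binomial chance of at least 6 patients is 0.196 (n = 20) to 0.267 (n = 22). Such rows would be listed only about 73 to 80% of the time.
- With 40 to 41 patients in the cohort, that chance of being shown would be 0.84 to 0.86.
- The SAP document history reports no responders in the interim data, so cohort 1 should have no responder-only rows.

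**4. When does a responder-only mean rise at all?**

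Let π be the responder share, G the baseline gap between responders and non-responders, and D the fall in every patient. Late mean minus baseline mean = (1 - π)G - D. With π = 0.20 and D = 5:

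| G | 0 | 5 | 10 | 15 | 20 |
|---|---|---|---|---|---|
| Apparent change | -5 | -1 | +3 | +7 | +11 |

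The sign turns only when G exceeds 5/0.8 = 6.25.

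**5. Does paired change remove the bias?**

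No. The -3 in step 1 is built in, because the expected change is the same for everyone. If the change itself (SD 10) correlates 0.3 with retention, the paired mean in those retained is -3 + 0.3 × 10 × φ(z)/q: -1.1, -0.1 and +0.8 at 60%, 40% and 25%.

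**The case against.** The strongest reply is that little is at stake. All analyses are exploratory (protocol 10.1), there is no QoL test or success claim, patient-level scores are listed, and the table layouts sit in separate mock documents that are not available here. That limits the severity. It does not make the rows comparable: n and a missing count remain cross-sectional, do not separate forms never due from forms not returned, and leave the pairing to the reader.

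Several stronger readings are tempting, and the documents do not support them:
- *Only means are reported.* SAP 8.1 also gives n, missing, SD, median and range.
- *Only responders give scores after week 17.* That describes the extension visits, but EOT QoL is scheduled for all patients. EOT falls at differing times, so it does not repair the visit rows either.
- *Visit 1 is restricted to patients with an old screening form.* Protocol 8.1.3 permits skipping the repeat; it does not bar it.
- *Large distortions of 5 to 10 points will be displayed.* They belong to the 25% case, which the more-than-5 rule would often keep out of the table in a cohort of 20 to 22.
- *Mean scores must rise.* Step 4 shows that they fall by the full decline when leavers and stayers start equal.

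**Conclusion.** The point holds as a missing analysis. The by-visit QLQ-C30 summaries compare different and selectively retained patients, and within-patient change is not requested although the SAP already defines it and uses it elsewhere. The rows can look better while individual patients worsen.

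A reader might infer that this bias is certain, or of known size. Neither follows. The figure of about +1 to +3.5 points against a true -3 at 60% retained assumes a baseline SD of 20, a correlation of 0.3 to 0.5 between baseline score and retention, and the same expected decline in everyone. The distortion most likely to reach the table comes from losses up to visit 9 rather than from responder-only extension rows. Since the analysis is exploratory and the remedy nearly free, this is an inexpensive improvement to the SAP, not a threat to the trial's conclusions.

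**What to change.** In SAP 8.4.5 and Table 14.6.6, add for each visit:
1. the change in the 0-100 scores from the last questionnaire before first dose (screening or C1D1), in patients with both values, naming this as the QoL baseline so that SAP 7.7.1 is unambiguous for this endpoint;
2. the number of forms expected under the schedule and the number received;
3. the baseline mean of the same patients, beside the visit mean.

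State in the text that this reduces but does not remove bias from selective dropout. There is no need to restrict which visits are shown; that would be a preference.

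The cost is a few columns in one table, the matching mock layout and a short SAP update before database lock. No new data and no extra patient burden are involved.

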## 8.5 Evaluation of Safety Endpoints

Analysis of safety endpoints will be based on the SES. Adverse events will be analyzed by relationship (Possible related, probable related and related will be considered as related to IMP) and severity (Grade 3 or higher according to CTCAE v5.0 will be considered as severe).

All results will be presented by treatment cohort (see 2.7).

### 8.5.1 Analysis of AEs

The analysis of AEs will be based on the SES. In this trial, only TEAE's (see section 7.7.12) will be analyzed. TEAEs will be classified by system organ class and preferred term using the Medical Dictionary for Regulatory Activities (MedDRA).

An overview of the subjects experienced an TEAE and the number of TEAE will be tabulated. Additionally, TEAE will be summarized by relation to IMP, toxicity (severity), special interest (AESI) and early toxicity.

Individual listings of AEs, SAEs and deaths will be generated.

TEAEs leading to premature discontinuation of study drug or withdrawal from the study will be listed in the same manner.

Table	
14.7.1	TEAEs by SOC and PT, overall
14.7.2	TEAEs by SOC and PT, by relationship
14.7.3	TEAEs by SOC and PT, by toxicity
14.7.4	TEAEs by SOC and PT, by early toxicity
14.7.5	TEAEs by SOC and PT, by special interest
Listing	
16.7.1	Adverse events
16.7.2	Serious adverse events
16.7.3	Adverse Events leading to discontinuation
16.7.4	Death

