5.1.3 Disease assessments in the primary phase of the treatment period (■■■■■)

After cycles ■ and ■ (i.e., at the beginning of cycles ■ and ■) response assessments will be carried out based on bone marrow and peripheral blood samples taken. For that, blood counts to assess potential cytopenias will be carried out and bone marrow and peripheral blood smears will be prepared to perform cytomorphology assessments.

Of these response assessments, the assessment at the end of ■■■■■ (performed at the beginning of cycle 5) is the primary endpoint (pEP) assessment.

Based on the outcome of the disease assessment in ■■■■■, if signs of disease progression are seen in the bone marrow, treatment with imetelstat will be stopped and the patient will undergo EOT and enter the follow-up phase.

Based on the outcome of the pEP (■■■■■) visit disease assessment, subjects will be either discontinued from treatment with imetelstat and enter the posttreatment follow-up phase (non-responders) or will continue treatment with imetelstat until loss of response/disease progression in the extension phase of the treatment period (responders) (see below at 5.1.4). In the absence of alternative treatment options, non-responders with stable or controlled disease may continue treatment in the extension phase at the investigator's discretion, in consultation with the sponsor, provided the disease remains controlled and none of the discontinuation criteria as described in section 7.7 are met. These subjects will follow the assessments and procedures according to the schedule of assessments for the extension phase (section VII, Part 2c). Responders who have BM blasts $\geq 5\%$ at the response assessment in cycle ■ will continue to receive imetelstat every ■ weeks. Responders who have BM blasts $<5\%$ at the response assessment in cycle ■ will continue to receive imetelstat every ■ weeks.

The disease assessment will be performed according to combined response criteria based on IWG 2018 criteria (MDS)¹ and the criteria of the European LeukemiaNet (AML)² in order to harmonize the criteria for MDS and AML patients in this trial. The combined criteria are listed in Appendix III a), section 16.3.

- Evidence of clinical benefit is defined as:
 - **At least partial remission (PR):**
 - This includes CR, CRi, PR and HI (any line) as per the combined response criteria used in this trial

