7.1.1 Treatment regimen prior to amendment to protocol version 5.0

The initial design involved all subjects receiving a starting dose of [REDACTED] mg/kg of imetelstat sodium given IV [REDACTED]. After [REDACTED] cycles of treatment, all subjects would undergo a response assessment according to the combined response criteria based on IWG 2018 criteria (MDS) and the criteria of the European LeukemiaNet (AML) as described in Appendix III: a). Subjects with at least a partial remission according to this criteria (PR, CR or CRi) would continue to be treated with imetelstat until loss of response/disease progression at which point they would undergo EOT and enter the follow-up phase of the trial. Non-responding patients at this response assessment would undergo EOT and enter the follow-up phase of the trial.

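### By-cohort TEAE tables use crude percentages and counts although AE observation time can differ between cohorts by rule; add rates per patient-month

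*SAP*

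**What the plan says.** SAP 8.5.1 plans the TEAE display in these words: "An overview of the subjects experienced an TEAE and the number of TEAE will be tabulated". The tables go by system organ class and preferred term: overall, by relationship, by toxicity grade, for early toxicity and for special interest (Tables 14.7.1-14.7.5). SAP 8.5 adds: "All results will be presented by treatment cohort". The default in SAP 8.1 is crude: "For categorical variables, the number (n) and percentage (%) of subjects per category will be the default summary presentation".

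The rules on staying on treatment changed between the cohorts.

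- **Earlier design (Protocol 7.1.1).** PR, CR or CRi was needed to continue. For everyone else: "Non-responding patients at this response assessment would undergo EOT and enter the follow-up phase of the trial". The SAP document history records no responders at the interim analysis.
- **Current design.** Hematologic improvement in any line now also counts as response (Protocol 2.3.1, 8.1.5). If no alternative treatment exists, "non-responders with stable or controlled disease may continue treatment in the extension phase" (Protocol 5.1.3). AE assessment is scheduled for these patients in Part 2c. Protocol 8.1.4 also requires a stop if progression is seen at the assessment after cycle 2. Protocol 7.1.1 mentions no such stop for the earlier regimen.

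Protocol 5.1.4 and SAP 2.1.4 say that data from continuing non-responders may be collected but will not affect the statistical analyses. No rule for any SAP table applies this.

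Best overall response runs from first dose to progression (SAP 7.7.8). For its display by cohort, SAP 8.4.3 says: "The summary table will include frequencies and percentages for each response category".

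**The concern.** The two cohorts are defined by dosing frequency (SAP 2.7). Protocol 7.2.2.1 links the frequency and severity of cytopenias to dose intensity, and Protocol 1.3.1 notes that more frequent dosing could aggravate neutropenia. The by-cohort TEAE tables are where a reader will look for that effect.

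A crude percentage rises with time under observation, and an event count rises in proportion to it. If one cohort is observed longer, its figures go up with no difference in risk; if many of its patients stop early, they go down. The planned exposure table does not repair this. Duration of treatment (SAP 7.7.3) ends no later than the last dose rather than at the end of AE collection, total dose is summed only to a set visit (SAP 6.2.3), and neither is used as a denominator.

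**Working it through.** **Inputs from the documents**

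- Primary assessment: visit 9, day 113 (Protocol schedule, Part 1), week 17 (Protocol 10.9.3).
- EOT: at most 14 days after the decision to stop (Protocol 5.1).
- AE recording: to 28 ± 5 days after the EOT visit (Protocol 9.3).
- Early assessment: after cycle 2, visit 5, week 9 (Protocol 8.1.4, SAP 8.3).

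**Step 1: the plan's own time point.** Week 5 is cycle 2, week 9 is cycle 3 and week 17 is cycle 5, so a cycle is 28 days. Then 4 × 28 + 1 = day 113, and 112/7 + 1 = week 17. This reproduces the plan.

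**Step 2: end of AE observation for a non-responder.** Take the decision as made on day 113.

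- Earliest: 113 + 0 + 23 = day 136; 136/7 = 19.4 weeks.
- Latest: 113 + 14 + 33 = day 160; 160/7 = 22.9 weeks.

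Waiting for results would move this later. For Cohort 1 the week is inferred, because the number of cycles in Protocol 7.1.1 is redacted. I use 21 weeks below.

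**Step 3: effect on crude figures when true risk is equal.** Assumptions, none of them in the documents: a constant hazard, the same in both cohorts; Cohort 1 observed for 21 weeks; in Cohort 2 a share f observed T weeks longer, and a share g stopping at week 9 with about 4 weeks of AE follow-up (13 weeks).

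For 30% incidence in 21 weeks, λ = -ln(0.70)/21 = 0.0170 per week. With I(w) = 1 - exp(-λw): I(13) = 0.198, I(21) = 0.300, I(33) = 0.429, I(47) = 0.550.

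- Cohort 2 crude incidence = (1 - f - g) × I(21) + f × I(21 + T) + g × I(13)
- Count ratio = [(1 - f - g) × 21 + f × (21 + T) + g × 13] / 21

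| f | T (weeks) | g | Cohort 2 crude | Difference (points) | Count ratio |
|---|---|---|---|---|---|
| 0 | - | 0 | 30.0% | 0 | 1.00 |
| 10% | 12 | 0 | 31.3% | +1.3 | 1.06 |
| 25% | 26 | 0 | 36.2% | +6.2 | 1.31 |
| 50% | 26 | 0 | 42.5% | +12.5 | 1.62 |
| 25% | 26 | 30% | 33.2% | +3.2 | 1.20 |
| 10% | 26 | 40% | 28.4% | -1.6 | 0.97 |

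Fourth row: 0.5 × 0.300 + 0.5 × 0.550 = 0.425. Last row: 0.5 × 0.300 + 0.1 × 0.550 + 0.4 × 0.198 = 0.284. Over the same rows the difference is -0.4 to +5.5 points at 10% incidence and -3.2 to +14.4 at 50%.

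**Step 4: the same rows per patient-time.** Expected events divided by observation time equals λ in every row, so the ratio between cohorts is 1.0, as it should be when risk is equal.

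**Step 5: is the top of the range plausible?** The fourth row needs half of Cohort 2 observed to 47 weeks, about 10.8 months. Protocol 1.1.1 cites median survival of 4 to 5.6 months after HMA failure in higher-risk MDS. Under exponential survival, 0.5^(10.8/4) = 15% to 0.5^(10.8/5.6) = 26% would be alive then. The fourth row is therefore an outer bound.

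**The case against.** The case against runs as follows.

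- **Status.** All analysis is exploratory (Protocol 10.1) and no between-cohort test is planned. In a cohort of 20, the evaluable number in Protocol 10.3, one patient is 5 points, and the exact 95% interval for 8/20 is about 19-64%. This stands. It limits the consequence to side-by-side reading, but these descriptive tables are the trial's safety result.
- **Time-aware analyses exist.** Table 14.7.4 covers early toxicity to visit 3, and Table 14.7.6 handles first related grade 3 or higher TEAEs by Kaplan-Meier with rates at fixed weeks. Protocol 10.9.3 also asks for unacceptable toxicity at weeks 4 and 17. This stands for those events. All other TEAEs after visit 3 remain uncovered.
- **Part 2c data are said not to affect the analyses.** If so, part of the imbalance disappears. But the Safety Evaluation Set is every dosed patient, and nothing tells the programmer to drop these events.
- **Direction.** A reader might infer that Cohort 2 must show more TEAEs by construction. The documents do not support that. The stop after cycle 2 shortens some Cohort 2 windows, and the last row in the working reverses the sign.
- **Length.** A reader might also infer that Cohort 1 observation ended at week 17 and that Cohort 2 is open-ended. Week 17 ends response assessment, not AE collection. For continued responders the end of study is reckoned at 6 months after the primary phase; only selected non-responders have no fixed end (Protocol 5.1, 10.12).
- **Best overall response.** Capping it at visit 9 is tempting, since Part 3 schedules no response assessment after EOT. A cap would contradict its definition and largely duplicate the primary endpoint, which is already a fixed-visit comparison by cohort.

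**Conclusion.** The concern holds for the main TEAE tables, as an inexpensive improvement. Crude by-cohort percentages and counts mix regimen with observation time, because the rules for continuing and stopping treatment differ between the cohorts.

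For an event of 30% incidence the distortion is about -2 to +13 points. The upper end is hard to reconcile with the survival figures that the protocol cites. The distortion is zero if nobody continues or stops early. The range rests on a constant, equal hazard, a 21-week Cohort 1 window inferred from the current schedule, and assumed continuation and early-stop shares.

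The documents do not show that the bias favors either cohort. Best overall response has the same unequal follow-up, but the fixed-visit primary endpoint already gives the like-for-like view, so a label is enough there.

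**What to change.** In SAP 8.5.1, keep the planned tables and add, by cohort:

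1. TEAEs per patient-month of AE observation, from first dose to the end of AE collection, for all TEAEs, grade 3 or higher, serious and AESI. Serious events are at present only listed, so that row is a new summary.
2. Observation time beside the rates: total patient-months, median and range.
3. A statement on whether events and patient-time from Part 2c enter these tables, consistent with the sentence in Protocol 5.1.4 and SAP 2.1.4.

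The denominator needs a single end date. Protocol 5.1.5 and 8.1.10 count AE collection from the last dose, whereas Protocol 9.3 counts it from the EOT visit; these should be reconciled first.

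In SAP 8.4.3, keep the definition of best overall response, label the by-cohort table as covering unequal follow-up, and point to Table 14.5.1 for the comparison at a fixed visit.

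A TEAE table limited to onset on days 1-113 is not a substitute: patients who stop early are still observed for less than that, and dose delays move visit 9 off day 113.

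The cost is a few more outputs from data already collected. A rate per patient-month assumes a roughly constant hazard; if events cluster early, a cohort with longer follow-up will look safer, so the rates should be read with the early-toxicity table. The analysis stays exploratory, with no between-cohort test.
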